## 12.0 Statistical considerations

All continuous variables will be examined for distributions and the presence of outliers. Variables that are not normally distributed will be transformed and if normality cannot be achieved, will be analyzed using non-parametric tests. Standardized descriptive statistics including measures of means, median, standard deviations, ranges, and standard errors for continuous variables within each group will be calculated to describe the groups at fixed time points. Differences between groups at baseline will be assessed by a one-way ANOVA. A repeated measures ANOVA will be used to evaluate the effects of diet, exercise, and their interaction (diet x exercise) on dependent variables; a significant interaction will be interpreted with a Bonferroni correction for multiple comparisons. A multivariate analysis that adjusts for the effects of confounding variables (age, sex, race, and baseline hepatic steatosis, hepatic insulin sensitivity, hepatokine profile, body weight, and body composition) will also be performed. Relations between continuous variables will be assessed by Pearson's or Spearman's correlation coefficients as appropriate. Data will be analyzed using SPSS software (SPSS, Chicago, IL).

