Subjects who meet all the inclusion/exclusion criteria will be invited to participate in the study. Eligible subjects will be randomized by way of a stratified random sample. The sample frame will be divided into strata based on BMI, sex, and age. Subjects from each stratum will then be randomized to 1 of 4 groups: 1) ADF, 2) aerobic exercise, 3) combination (ADF plus aerobic exercise), or 4) control. **A total of n = 360 subjects (n = 90 per intervention group) will be recruited.** All the subjects will have the right to withdraw from the study at any time.

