### **Exercise protocol**

[figure not shown]
**Exercise group and combination groups:** Only combination and exercise groups will partake in the exercise training. All training sessions will be conducted at the subject's home. Subjects will participate in a supervised aerobic exercise program 5 times per week, 40-60 min/d, for 24 weeks. Exercise will be performed by watching YouTube aerobic exercise (Zumba) videos at home. The video links will be provided by the study coordinator prior the exercise session. The coordinator conducting the study session on Zoom will have immediate knowledge of the subject's location so that they can relay this information to emergency personnel if needed. During the week 1 sessions, subjects will exercise for 40 minutes at a moderate intensity (65% heart rate max (HRmax)). During the week 2 sessions, subjects will train for 50 minutes at a higher intensity (75% HRmax). For weeks 3-24, subjects will train for 60 minutes at an even higher intensity (85% HRmax). The participants will wear heart rate monitors (Fitbit Alta HR, Boston, MA) during each training session to provide visual feedback of their individualized target heart rate. Fitbit monitors will be distributed to subjects so that they can monitor their heart rate at home. **Compliance with the training:** A research assistant will be present to supervise all the training sessions over Zoom. All sessions will be pre-scheduled with the research assistant so the participant knows when to enter the Zoom meeting to perform the activity. Exercise will be carefully documented through regular online attendance at the training sessions. Subjects will be permitted to choose the day and time slot that works best for them. If a subject misses their session, they will be required to make up for it that same week. Subjects will be permitted to miss 5 sessions total during the 24-week trial.

**ADF group and control groups:** ADF and control subjects will be asked to maintain their regular daily activity habits during the study. They will not participate in the exercise protocol.

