**Hepatic steatosis by magnetic resonance spectroscopy (MRS):** MR scans will be performed at the Center for Magnetic Resonance Research (CMRR). MR images and spectrum will be acquired using a 3.0 T MR scanner. MR examinations will be performed by experienced MR technologists. Subjects will arrive at the CMRR in the morning following an overnight (8 h) fast. Total hepatic triglyceride content will be assessed at week 1, 13 and 24 by H MRS. A body array MRI coil will be affixed to each subject's back and aligned with the subject's spine and shoulders for accurate repositioning of repeat scans. Each subject will be positioned face down and head first in the scanner on a memory foam mattress to minimize respiratory motion. An 8 cm^3 voxel is positioned within the right posterior lobe of the subject's liver with guidance from the high-resolution localization images. Manual shimming will be performed to a line width of ~40Hz to ensure high quality spectra. MR spectra with and without water suppression will be acquired with a single-voxel PRESS acquisition with a long repetition time (TR=5000ms), and a short echo time (TE=30ms) to limit the effects of magnetic relaxation. The acquisition will be obtained with 32 averages to obtain sufficient signal, and the data will be Fourier-Transformed, filtered, baseline corrected, and phased. Areas of resonances from protons of water and methylene groups in fatty acid chains of the hepatic triglyceride will be evaluated with a line-fit procedure and commercial software (NUTS-ACORNNMR, CA).

**Blood sampling:** Twelve-hour fasting blood samples will be collected at week 1, 13, and 24 consecutive feed and fast days (20 ml at each time point). All blood draws will be performed at the HNRU by [name]. Blood will be centrifuged for 15 min at 520 x g and 4°C to separate plasma from red cells, and will be stored at -80°C at the HNRU. Specimens will be labeled with the subject ID and study week, and will be stored until the study is completed. After the study is over, all specimens will be destroyed.

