## 9.0 Data analysis

Data will be analyzed by [name] PhD (Biostatistician) and [name] by SPSS software (SPSS v24).

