screening appointment (e.g. dietary protocol, exercise intervention, time commitment, etc.), and will be free to withdraw from the study at any point. There are no known hazards to MRS examination other than the discomfort associated with confinement and remaining stationary for the duration of the study. Testing of all subjects will be terminated immediately should they become distressed. We will carefully screen out individuals who have an implanted electrical device (such as a cardiac pacemaker or a neurostimulator), or a certain type of metallic clip (i.e., an aneurysm clip in the brain). These devices can malfunction and cause harm to the patient in the magnet environment. We will also carefully screen individuals who are claustrophobic to reduce any adverse events. Loss of confidentiality may also be a risk. To protect subject identity, only code numbers (i.e. randomly generated numbers) will identify all laboratory specimens, evaluation forms, reports, and other records. Risk of participating in the exercise program includes: muscle/joint strains, sprains, or injury. If a subject is injured during the exercise session, they will be asked to stop exercising immediately and rest. The muscle/joint will be iced and elevated, and the subject will be sent home with a small ice pack and asked to ice/elevate the area for 20 minutes every hour to alleviate pain and inflammation. A cardiac event may also occur as a result of participating in the exercise program. If this occurs, 911 will be immediately called by the research assistant who is supervising the exercise session and the subject will be treated by a medical professional.

**Adverse Event Grading Scale:** Because only minor adverse events related to blood drawing, DXA scanning, MRS scanning, alternate day fasting and exercise may occur, no grading scale is necessary.

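### The plan sets no analysis population or missing-data rule, and its repeated-measures ANOVA by default drops anyone missing an entered visit; an all-randomised mixed model in SPSS would keep them

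*Combined protocol and SAP*

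**What the plan says.** Section 12.0 is the whole analysis plan, and section 9.0 adds only the analysts and SPSS v24. The one named test of the treatment effect is in section 12.0: "A repeated measures ANOVA will be used to evaluate the effects of diet, exercise, and their interaction". Pairwise comparisons follow: "a significant interaction will be interpreted with a Bonferroni correction for multiple comparisons". Two further routes are mentioned without a model or a missing-data rule: non-parametric tests where normality cannot be achieved, and "A multivariate analysis that adjusts for the effects of confounding variables".

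On the data, section 6.0 says of the MRS outcome: "Total hepatic triglyceride content will be assessed at week 1, 13 and 24". The plan does not say which of these visits enter the ANOVA.

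On withdrawal, section 5.0 says "All the subjects will have the right to withdraw from the study at any time", and section 11.0 says participants "will be free to withdraw from the study at any point". Section 6.0 permits five missed exercise sessions but does not say how someone who misses more is analysed. No section defines an analysis population, a missing-data method, a dropout allowance, or outcome measurement after a participant stops fasting or exercising.

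**The concern.** Conventional repeated-measures ANOVA needs a complete row for each participant, so collected data go unused whichever visits are entered. With three visits entered, one missed week-13 scan removes a participant who has both baseline and week-24 scans. With only weeks 1 and 24 entered, the week-13 values of those who later withdraw are unused. The adjusted analysis may lose more people, because it lists at least 14 baseline covariates: age, sex and race (3), steatosis and insulin sensitivity (2), the seven hepatokines of Hypothesis 2 (7), body weight and body composition (2).

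Two things are at stake. Precision is lost even if every loss is random. If loss also differs between arms and is related to response, the combination contrasts in Hypotheses 1 to 3 are biased among completers. The arms do differ in burden. In two of them, "Subjects will participate in a supervised aerobic exercise program 5 times per week, 40-60 min/d, for 24 weeks", which is 5 × 24 = 120 sessions; two arms fast, and control does neither. Because the population is not fixed, the choice between all randomised, completers and adherers could also be made after the data are seen.

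**Working it through.** **Inputs from the documents.** 360 randomised, 90 per arm (section 5.0); the intervention table in section 6.0 gives 45 per arm, a conflict to be reconciled separately, so both are used below. MRS at weeks 1, 13 and 24. No dropout rate, SD, effect size, alpha or power is given, so the 360 cannot be reproduced.

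**Assumptions.** Equal correlation ρ = 0.7 between visits, SD = 1 at each visit, baseline observed for everyone.

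**1. Precision under random loss.** The completers' variance of mean week-24 change in one arm is 2(1 − ρ)/n_c, with n_c the number of completers. The mixed-model variance is c′I⁻¹c, with c = (−1, 0, 1) and I the sum over missingness patterns of (number with that pattern) × (inverse covariance of the visits observed). Example, 10% withdrawing before each follow-up visit: n_c = 0.9 × 0.9 × 90 = 72.9; completers 0.6/72.9 = 0.00823; mixed model 0.00788; ratio 1.045; effective n = 0.6/0.00788 = 76.2.

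Power is for a contrast with 80% power at 90 complete per arm: Φ(2.80 × √(n/90) − 1.96). For n = 72.9 this is Φ(2.52 − 1.96) = 71.3%.

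| Random loss, 10% (20%) | Completers n | Mixed-model effective n | Variance ratio | Power, completers vs mixed model |
|---|---|---|---|---|
| Withdrawal before each follow-up | 72.9 (57.6) | 76.2 (62.8) | 1.045 (1.090) | 71.3 vs 73.2% (61.1 vs 64.8%) |
| Withdrawal in total, half before week 13 | 81 (72) | 82.9 (75.5) | 1.023 (1.048) | 75.7 vs 76.7% (70.7 vs 72.8%) |
| Independent misses, three visits entered | 72.9 (57.6) | 83.3 (76.0) | 1.143 (1.320) | 71.3 vs 76.9% (61.1 vs 73.1%) |
| Independent misses, weeks 1 and 24 entered | 81 (72) | 83.3 (76.0) | 1.029 (1.056) | 75.7 vs 76.9% (70.7 vs 73.1%) |

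For ρ from 0.8 to 0.5, the first-row ratio runs from 1.038 to 1.059 (1.077 to 1.119).

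**2. Bias among completers.** Simulation with four arms, no true difference, 90 per arm and 6,000 replicates. Participants leave after week 13 with probability 2 × rate × rank of poor week-13 change. A negative sign favours the combination over ADF. Results are for combination loss of 20/30/40%.

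| Loss pattern | Combination − ADF bias (SD) | Interaction test at nominal 5% | Planned sequence declares a difference |
|---|---|---|---|
| Equal in all arms | 0 | – | about 0.5% |
| Graded (exercise 0.75×, ADF 0.5×, control 10%) | −0.03/−0.06/−0.09 | 4.8/5.0/5.7% | 0.4/0.7/1.3% |
| Extreme (response-linked in combination only, random 10% elsewhere) | −0.06/−0.09/−0.14 | 6.2/8.4/11.8% | 0.7/2.0/3.7% |

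The planned sequence is read as a significant interaction followed by a pairwise test at 0.05/6, six pairs being assumed. At 45 per arm the bias is the same and the extreme interaction rate is 5.4/6.5/8.1%.

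A separate two-arm simulation (1,500 runs, true difference −0.25 SD, about 20% and 17% lost, a different assumed link to week-13 change) gave −0.349 for completers and −0.249 for the likelihood estimate. The size of the bias therefore depends on the assumed link.

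**3. What the mixed model does not remove.** Extreme pattern, 20/30/40%:

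| Loss depends on | Completers (SD) | Mixed model (SD) |
|---|---|---|
| Observed week-13 change | −0.06/−0.09/−0.14 | 0.00 |
| Week-13 change, half the loss before week 13 | −0.05/−0.09/−0.14 | −0.01/−0.03/−0.04 |
| Week-24 change itself | −0.11/−0.19/−0.29 | −0.08/−0.14/−0.21 |

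**The case against.** The strongest reply is that the plan orders no deletion. It names no SPSS procedure, and a mixed-model form of repeated-measures analysis would fit its wording. Nor does it end measurement when someone stops exercising or fasting: DXA is scheduled for all subjects, and withdrawal as described is from the study. This is right as far as it goes. The plan is silent rather than exclusionary, and the silence is the main defect.

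The second reply is that the harm is small. Under random withdrawal the avoidable cost is 1 to 4 power points, and most of the lost power is lost under either method. With burden-graded loss the interaction test stays at 5 to 6%. Clear inflation needs the extreme pattern, in which ADF and exercise lose people only at random although each shares a burden with the combination. The plan also supports retention: home sessions over Zoom at chosen times, same-week make-up, prorated payment, and control visits at the same frequency. All of this stands. Unequal or response-related loss, and its direction, are assumptions that the documents do not show.

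Third, changing the ANOVA leaves the non-parametric route without a missing-data rule, and inviting people back takes real work. Both points are fair and are met in the fix.

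**Conclusion.** The concern holds. No section sets an analysis population or a missing-data rule, and the only named test conventionally leaves collected scans unused. The likely harm is modest. With ρ = 0.7 and 10 to 20% random loss, the avoidable cost is 1 to 4 power points in most patterns; it reaches 6 to 12 only if three visits are entered and misses are independent. Completers' bias is zero with equal loss, 0.03 to 0.09 SD with graded loss and 0.06 to 0.14 SD in the extreme case, when loss follows week-13 change; it is larger if loss depends on week-24 change itself. The planned interaction-then-Bonferroni sequence stays below 5% false declarations for combination versus ADF in every week-13-linked pattern simulated at 90 per arm. All these sizes rest on assumed dropout rates, correlation and loss mechanisms. That the omission exists does not rest on them. The plan should be changed because a better method is available in the same software and because who is analysed should be fixed in advance.

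**What to change.** In section 12.0:

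- Define the analysis population as all randomised participants in their assigned arm, whether or not they missed sessions or stopped the intervention.
- Replace the repeated-measures ANOVA with a likelihood-based linear mixed model (SPSS MIXED) with visit, diet, exercise and their interactions. Use every observed week-1, 13 and 24 value, with baseline modelled as an outcome. State the covariance structure, and name the week-24 combination-versus-ADF and combination-versus-exercise contrasts.
- State the model type and missing-covariate handling for the adjusted analysis, and a missing-data rule for any outcome sent to non-parametric tests.
- Invite those who stop the intervention to the already scheduled week-24 assessment, and report loss by arm.
- Keep the completers' analysis as a sensitivity analysis. Add a missing-not-at-random analysis, for example shifting missing week-24 values in one arm by increasing amounts, because the mixed model removes the bias only under missing at random.

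Two limits remain: participants seen only at baseline add little, and a missing covariate still excludes unless its handling is specified.

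The cost is a rewording of section 12.0, a different procedure in the same software, some extra analysis, and the effort of bringing people back for a visit that includes MRS, DXA and OGTT. No arm, visit or treatment rule changes.

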## 3.0 Objective/Aims

**Specific aim 1:** To compare the effects of a combination intervention (ADF and aerobic exercise) versus ADF or exercise alone on hepatic steatosis over 24-weeks in prediabetic obese NAFLD subjects.

**Hypothesis 1:** The combination group will experience greater reductions in hepatic steatosis (measured by MRS) when compared to the ADF group and the aerobic exercise group.

**Specific aim 2:** To compare the effects of a combination intervention (ADF and aerobic exercise) versus ADF alone or aerobic exercise alone on hepatokine profile over 24-weeks in prediabetic obese NAFLD subjects.

**Hypothesis 2:** The combination group will experience greater decreases in hepatokines with negative metabolic actions (fetuin-A, fetuin B, FGF-21, RBP4, selenoprotein P) and greater increases in hepatokines with positive metabolic actions (SHBG, adiponectin) when compared to the ADF group and the exercise group.

**Specific aim 3:** To compare the effects of a combination intervention (ADF and aerobic exercise) versus ADF alone or aerobic exercise alone on hepatic insulin sensitivity, insulin resistance, HbA1c, and other metabolic disease risk variables over 24-weeks in prediabetic-obese NAFLD subjects.

**Hypothesis 3:** The combination group will experience greater improvements in hepatic insulin sensitivity, insulin resistance and HbA1c and other metabolic disease variables (fasting glucose, insulin, plasma lipids, blood pressure, TNF- $\alpha$ , IL-6) when compared to the ADF group and the exercise group.

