**Metabolic disease risk factors:** Plasma metabolic disease risk factors will be assessed at baseline week 1, 13, and 24. Plasma total cholesterol, LDL cholesterol, HDL cholesterol, and triglyceride concentrations will be measured in duplicate using enzymatic kits, standardized reagents, and standards (Biovision Inc, Mountainview, CA) and analyzed using a microplate reader (iMark Microplate Reader; Bio-Rad Laboratories Inc, Richmond, CA). HbA1c will be assessed by ELISA (Mybiosource, San Diego, CA). Fasting plasma glucose concentrations will be measured with a hexokinase reagent kit in duplicate (A-agent glucose test, Abbott, South Pasadena, CA). Fasting insulin will be measured as total immunoreactive insulin (Coat-A-Count Insulin, Los Angeles, CA). Insulin resistance (IR) will be calculated by the HOMA (Homeostasis Model Assessment) method:  $[HOMA-IR = \text{Fasting insulin } (\mu\text{U/ml}) \times \text{Fasting glucose } (\text{mg/dL}) / 405]$ .

**Proteomics and metabolomics:** Plasma-derived proteomic and metabolomic outcomes will be measured using immunoassay and mass spectrometry, as described previously.

**Hepatokine plasma levels:** Plasma hepatokines will be measured at week 1, 13, and 24. Commercially available ELISA kits will be used to measure concentrations of Fetuin-A, fetuin-B, FGF-21, SHBG, and RBP4, (R&D Systems, Minneapolis), and adiponectin and selenoprotein P (Mybiosource, San Diego, CA). All samples will be assessed in duplicate.

**Inflammation:** Inflammatory markers will be measured at week 1, 13, and 24. C-reactive protein (CRP) will be measured in duplicate using Immulite 1000 High Sensitivity CRP kits (Diagnostic Products Corporation, Los Angeles, CA). Adiponectin, leptin, TNF- $\alpha$ , and IL-6 will be measured using ELISA (R&D Systems, Minneapolis, MN).

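### Section 12.0 names no visit interaction, visit list or week-24 contrast for the repeated measures ANOVA, so its tests as worded do not address the hypothesised reductions over 24 weeks

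*Combined protocol and SAP*

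**What the plan says.** The analysis plan is one paragraph, Section 12.0 (Statistical considerations). Section 9.0 adds only who will analyse the data and with which software. The main model is described in one clause: "A repeated measures ANOVA will be used to evaluate the effects of diet, exercise, and their interaction (diet x exercise) on dependent variables". The only interaction mentioned there is diet by exercise, and it is the one to which the Bonferroni correction is attached. Visit or time does not appear as a factor, and the paragraph does not say which visits are responses.

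Baseline is mentioned twice more in Section 12.0: "Differences between groups at baseline will be assessed by a one-way ANOVA", and an additional analysis described as "A multivariate analysis that adjusts for the effects of confounding variables (age, sex, race, and baseline hepatic steatosis, hepatic insulin sensitivity" and further baseline measures. The visit at which that adjusted analysis takes its outcome is not stated.

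Section 6.0 sets the measurement times. For MRS: "Total hepatic triglyceride content will be assessed at week 1, 13 and 24". For the metabolic risk factors, week 1 is labelled as baseline: "Plasma metabolic disease risk factors will be assessed at baseline week 1, 13, and 24".

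Section 3.0 sets the question. Aim 1 concerns effects "on hepatic steatosis over 24-weeks", and Hypothesis 1 reads: "The combination group will experience greater reductions in hepatic steatosis (measured by MRS) when compared to the ADF group and the aerobic exercise group". Hypotheses 2 and 3 are likewise worded as greater decreases, increases or improvements in the combination arm than in each single-intervention arm.

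**The concern.** A greater reduction is a between-arm difference in change. In a repeated measures ANOVA that difference sits in the interactions of diet, exercise and diet x exercise with visit, or in a contrast at a chosen visit. The terms that Section 12.0 names are between-subject terms: they compare the arms on each participant's average over the visits in the model. If week 1 is one of those visits, the average includes a measurement at which randomised arms have no expected difference, and the tested effect shrinks accordingly.

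The stakes are twofold. First, a real effect at week 24 may be reported at a fraction of its size and tested with much less power. Second, standard output for this model gives both the between-subject tests and the by-visit tests. Because the plan does not say which is the result, the choice can be made after the data are seen. The same sentence governs steatosis, the hepatokines and the metabolic outcomes, so the gap covers all three aims. It concerns the time dimension and is separate from the question of which arms are compared.

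**Working it through.** **What can be reproduced.** The only design figure is the sample size: 4 x 90 = 360 (Section 5.0). The documents give no alpha, power, effect size, SD, within-person correlation or dropout rate, so there is no power statement to reproduce.

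**Inputs from the documents.** Three MRS visits, at weeks 1, 13 and 24, with week 1 as baseline (Section 6.0). Named terms: diet, exercise, diet x exercise (Section 12.0). 90 per arm (Section 5.0).

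**Input not in the documents.** f, the share of the week-24 effect d present at week 13.

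**Step 1: effect tested.** With expected effects 0, f·d and d at the three visits, the between-subject term estimates (0 + f·d + d)/3 = d(1+f)/3. The loss is 1 − (1+f)/3. With weeks 13 and 24 only, the average is d(1+f)/2 and the loss is 1 − (1+f)/2.

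| f | Loss, weeks 1, 13, 24 | Loss, weeks 13 and 24 only |
|---|---|---|
| 0 | 67% | 50% |
| 0.25 | 58% | 38% |
| 0.5 | 50% | 25% |
| 0.75 | 42% | 13% |
| 1 | 33% | 0% |

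If visit interactions are fitted and week 24 minus week 1 is read, the loss is 0% for every f.

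**Step 2: simulation check.** 2x2 design, 90 per arm, correlation 0.7, 2,000 runs, true week-24 effect −0.50:

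| Quantity estimated | f = 0.5 | f = 1 |
|---|---|---|
| Between-subject term, three visits | −0.252 | −0.331 |
| Same, with week 1 also a covariate | −0.250 | −0.332 |
| Week-24 change contrast | −0.497 | −0.500 |
| Baseline-adjusted week 24 | −0.498 | −0.500 |

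Adjusting for baseline does not remove the dilution while week 1 stays among the averaged responses.

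**Step 3: power, as an illustration.** Assumed: d = 0.5 SD, equal correlation r = 0.7 between visits, two-sided 5%, no dropout, one pairwise comparison of 90 v 90 without Bonferroni correction. Power ≈ Φ(effect/SE − 1.96), with SE = √(2V/90).

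- Three-visit average: V = (1+2r)/3 = 0.80, SE = 0.133. At f = 0.5 the effect is 0.25, the ratio 1.875 and power 47%. At f = 1 the effect is 0.333, the ratio 2.50 and power 70%.
- Week-24 change from week 1: V = 2(1−r) = 0.60, SE = 0.115, ratio 4.33, power 99%.
- Week 24 adjusted for week 1: V = 1−r² = 0.51, SE = 0.106, ratio 4.70, power above 99%.
- Week 24, unadjusted: V = 1, SE = 0.149, ratio 3.35, power 92%.
- Mean of weeks 13 and 24 adjusted for week 1: V = (1+r)/2 − r² = 0.36, SE = 0.089. At f = 0.5 the effect is 0.375, the ratio 4.19 and power 99%.

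The intervention table in Section 6.0 gives 45 per arm, which conflicts with the 90 in Section 5.0 and must be reconciled. It does not alter the ratio (1+f)/3. At 45 per arm the three-visit average has 26% (f = 0.5) or 42% (f = 1) power, the week-24 change 86% and the adjusted week-24 contrast 91%.

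**The case against.** The strongest reply is that the sentence is shorthand. A repeated measures ANOVA has a within-subject factor by definition, and with outcomes at weeks 1, 13 and 24 that factor can only be visit. An analyst may well intend to fit the interactions with visit and read those. Section 12.0 also handles baseline separately in two places, which fits a model with week 1 as covariate and weeks 13 and 24 as responses. Under that reading nothing from week 1 is averaged in, and power in the illustration is about 99% even at f = 0.5. Nor do the documents fix a week-24 difference as the estimand: the aims speak of effects over 24 weeks, so an average over visits is a different quantity rather than a biased estimate of a declared one.

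Much of this stands. A reader might infer that the plan does average week 1 into the effect and will understate the 24-week result by a third to a half. The documents do not support that as fact: they neither say that week 1 is a response nor give f, and other readings give a smaller loss or none. It is also fair that the power comparison mixes dilution with the gain from using baseline. The unadjusted week-24 figure of 92% shows that most of the gap in this illustration is dilution, but every power figure rests on assumed inputs.

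What does not stand is that no change is needed. The shorthand reading is not written down, and the one interaction that is defined is diet x exercise. The usual joint group-by-visit test is still not the week-24 difference. The additional baseline-adjusted analysis names no outcome visit and, as the simulation shows, would not remove the dilution if week 1 remained among the responses.

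**Conclusion.** The concern holds in conditional form. As worded, Section 12.0 names between-subject tests that do not address the hypothesised differences in reduction, and it leaves the visits entered and the week-24 contrast undefined. This follows from the text alone.

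The size depends on the reading. With all three visits averaged, the tested effect is (1+f)/3 of the week-24 effect: a loss of one half at f = 0.5 and one third at f = 1, and larger if less than half the effect is present at week 13. With weeks 13 and 24 only, the loss is 25% to 0% for f from 0.5 to 1. With visit interactions and the week-24 contrast, it is nil. These ratios assume no expected difference between arms at week 1. The power contrast of 47% or 70% against about 99% only illustrates what the literal three-visit reading could cost; it does not estimate this trial's power.

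**What to change.** Amend Section 12.0 as follows:

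- State that week 1 is the baseline and is not averaged into any tested treatment effect.
- Specify the model: either visit, diet, exercise, diet x exercise and the interactions of each treatment term with visit; or weeks 13 and 24 as responses, with the week-1 value as covariate and treatment effects allowed to differ by visit.
- Name the baseline-adjusted week-24 difference as the test for each hypothesis, for combination v ADF and for combination v exercise, with week 13 secondary.
- State that effects averaged over visits including week 1 will not be used as evidence for Aims 1 to 3.
- Say at which visit the additional covariate-adjusted analysis takes its outcome.

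The cost is wording only. Data collection, visits and sample size are unchanged, and the planned software can fit either model. The change should be made before outcome data are examined by arm.
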